5.0 DATA COLLECTION AND MANAGEMENT

5.1 Data Procurement

- Participant data will be collected by study principal investigator and co-investigators and the research coordinator.
- Participants taking study COC will keep a dairy to indicate daily adherence
 - COC diaries will be reviewed at each visit to assess patterns of day-to-day COC use.

5.2 Variables Collected

The following data points/variables will be collected:

- ID number
- Date of birth
- Medical history
- Surgical history
- Menstrual/gynecologic history
- Medications currently taking
- Social history
- Serum relaxin level
- Laxity measurements: Beighton score and anterior and posterior knee displacement (mm) during KT-2000
- Patterns of day-to-day COC use (i.e., consecutive days of OCP use reported with no more than two consecutive days of nonuse)
- Trunk flexion hip adduction, and internal/external and coronal plane rotation of the knee measured during a singled-legged drop using the motion tracking equipment mentioned above in section 4.0 (Aim 2).

5.3 Source Documents

All data for this study will be collected prospectively. Subjects' EMR or other external sources will not be accessed for use in the study.

5.4 Data Collection and Storage

Study documents will be filled out electronically the day of the visit by the investigator and/or coordinator. The documents will be labeled with a unique study ID number rather than any direct subject identifier. After signature of the study PI, data will be entered into the secure REDCap database by the research coordinator.

5.5 Confidentiality and Security of Data

Data will be coded; subject identifiers will be removed from the rest of the data and a unique study ID number assigned. The list linking identifiers to the study ID number will be kept at CSMC and will not be shared externally. This linking list will be kept in case of incidental findings. This linking document will be kept on a locked excel sheet that only the PI and research coordinator will have access to.

6.0 DATA AND SAFETY MONITORING

6.1 Data and Safety Monitoring Plan

- Only listed study staff will have access to the processed data gathered from the visits.
- Any analysis of the data will be performed on the de-identified dataset.
- As above, data from the samples will be kept and stored in the Kerlan Jobe secure network only.

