4.0 STUDY DESIGN AND METHODS

Data will be collected prospectively throughout participant intake and study progression. Given the personal nature of women's contraceptive preferences, we will enroll three categories of female athletes:

- (1) Women who are not on hormonal contraception and have no plan to start in the next year
- (2) Women who are not on hormonal contraception and would like to initiate study COC
- (3) Women who are currently on hormonal contraception and would like to switch to study COC

For those participants who would like to start study COC, women will be prescribed a daily oral contraceptive containing ethinyl estradiol 20mcg/norethindrone 1mg.

Women will maintain a contraceptive compliance diary via paper or Word document which they can submit to us in person or electronically. Orthopedic testing will start during the fourth menstrual/COC cycle due to delay in COC effect and theoretical cumulative protective effect of COC use. All three groups will undergo below testing to evaluate primary and secondary aims.

Serum Relaxin (Aim 1):

- Participants will have about 2ccs of blood drawn to measure serum relaxin levels at two time points:
 1. Baseline
 2. Fourth month of study participation - menstrual cycle-specific timing:
 - Participants not on COC:
 - Luteal phase of their menstrual cycle (Days 14-28)
 - This is when peak relaxin levels are noted to occur
 - Participants on COC:
 - Pill pack days 14-28
 - Women on COC have suppressed ovulation and thus no true luteal phase, but will undergo testing during the same time period

Joint Laxity (Aim 2):

- Joint laxity will be tested at two separate time points:
 1. Baseline
 2. Fourth month of study participation – synced with serum collection for relaxin level testing.
- Joint Testing:
 - Each participant's bilateral knee joint laxity will be tested using a KT-2000 arthrometer (Medmetric Corp, San Diego, CA) for anterior and posterior laxity.
 - Laxity and biomechanical testing will be done in the athletes' training room on campus.
 - To eliminate inter-rater differences in the laxity measurement, only one examiner will conduct all knee laxity measurements.

- With a passive anterior and posterior drawer test at 67N and 87N, an average displacement (mm) for three cycles will be determined.
- A Brighton score will be calculated with goniometer by a one examiner to assess generalized hypermobility at each time point.

Motion Tracking Analysis (Aim 2):

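### The study prescribes a COC, but the plan specifies no systematic adverse-event collection and no date or reason for stopping it

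*Combined protocol and SAP*

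**What the plan says.** Section 4.0 makes the drug part of the study. For participants who opt for it, "women will be prescribed a daily oral contraceptive", and prescribing is a row in the schedule of procedures, which labels every procedure as research related.

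Section 6.1 has three items. The first is on access: "Only listed study staff will have access to the processed data gathered from the visits". The second is on de-identification: "Any analysis of the data will be performed on the de-identified dataset". The third is on storage: "data from the samples will be kept and stored in the Kerlan Jobe secure network only".

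Section 5.2 opens with "The following data points/variables will be collected" and then itemises. Two of its items bear on COC use: "Patterns of day-to-day COC use (i.e., consecutive days of OCP use reported with no more than two consecutive days of nonuse" and "Medications currently taking". It also lists medical history and menstrual and gynecologic history. It names no adverse event, no serious adverse event, and no date or reason for stopping.

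The plan has four routes of contact after enrolment:
- a COC diary, of which Section 5.1 says "COC diaries will be reviewed at each visit to assess patterns of day-to-day COC use";
- the Section 5.2 history items, asked again at the 4-month visit;
- an interval medical history at the 4-month visit and the one-year call;
- weekly training-room follow-up, which asks about injury.

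Section 5.3 rules out the use of medical records or other external sources. Section 7.1 (Study Outcome Measures) contains no safety outcome.

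**The concern.** A study that prescribes a drug would normally say which harms it records, when it asks, and who looks at them. Here the section whose title promises safety monitoring deals only with data handling, and the variable list does not make up for it.

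Two things are at stake. First, Aim 3 asks whether COCs protect against injury, and the background section hopes to add to the evidence on their non-contraceptive benefits. A favourable result could not be set beside any systematic account of harm in the same women. Second, when a participant stops the COC, the plan has no field for the date, which matters for classifying exposure, and none for the reason, which is needed to tell a side-effect stop from any other. Because external records are excluded, what is not asked at the time cannot be filled in from them later.

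**Working it through.** The plan gives no safety figure to reproduce. The check is a reading of each route by which a harm or a stop could reach the dataset, plus some simple arithmetic on size.

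**Routes for harms**
- Interval medical history (Section 4.0 schedule): at month 4 and one year. It could bring out a significant event, but its content is not defined and it is not itself an item in Section 5.2.
- Repeat medical and gynecologic history (Sections 4.0 and 5.2): at screening and month 4 only. It could show a new condition, but does not ask about adverse events as such.
- Weekly follow-up (Section 4.0): frequent, but about injury.
- External records (Section 5.3): closed.

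**Routes for stops**
- Diary (Sections 4.0, 5.1 and 5.2): a stop appears as a run of non-use, and its date could be read off if the diary is kept and handed in. The reason could not.
- Current medications (Section 5.2): could show at month 4 that the COC is no longer taken, without date or reason.

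**Timing of diary review**
The Protocol Summary gives two in-person visits and one phone call over 12 months. The schedule makes these screening, month 4 and the one-year call. At screening there is no diary yet, so month 4 is the only in-person review after the COC starts. The interval from then to the call is 12 − 4 = 8 months, or 8/12 = 67% of the study period. Injuries are tracked throughout it. If the phone call counts as a visit for diary review, there is one further review, at the end of those eight months. Diaries may be submitted electronically, but no review between the two contacts is scheduled.

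**Number exposed**
Section 7.1 (Sample Size Considerations) assumes equal groups and a total of 140; Section 3.1 aims for 150.
- 140/2 = 70
- 150/2 = 75

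Groups form by participants' own choice in a convenience sample, so 70 to 75 is an assumption.

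**What full capture could show**
If no event of a given kind were seen in n women, the one-sided 95% upper limit on its risk is 1 − 0.05^(1/n).
- n = 70: 1 − 0.05^(1/70) = 4.2%
- n = 75: 1 − 0.05^(1/75) = 3.9%

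Even complete data would therefore support description, not a finding that rare harms are absent.

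**The case against.** The strongest reply is that the plan is not blind. A daily diary is kept, current medications are asked again at month 4, and an interval history is taken twice. A reader might infer from Sections 5.2 and 6.1 that harms and stops will go wholly unrecorded. The documents do not support that: stops would show as non-use, and a serious harm could well emerge in the interval history. This part of the objection stands and limits the point to the lack of systematic, defined collection.

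It is also fair to say that exposure classification depends on whether and when the COC was stopped, not on why. The date therefore serves exposure, and the reason serves safety. The diary can supply the date only while it is kept and reviewed, which is unclear after month 4.

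A second tempting inference is a loss of power. Suppose 10% of COC users stopped and returned to the 30% risk. The COC-group risk would be 0.9 × 10% + 0.1 × 30% = 12%, and continuity-corrected power at 70 per group would fall from 0.79 to 0.68. The documents give no stop rate, and the loss comes from the stopping itself: it would occur whether or not reasons were recorded. It is no measure of this gap.

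Finally, the aims concern relaxin, laxity and injury; no benefit–harm conclusion is planned; women with a contraindication are kept out of the COC group; and adverse-event procedures may sit in consent or institutional documents not supplied here. The absence is therefore asserted only for the protocol text. Screening for contraindications acts at entry and records nothing afterwards. If procedures do exist elsewhere, a cross-reference in Section 6.1 would settle much of the point.

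**Conclusion.** The point holds in limited form and should be fixed. The protocol prescribes a COC, yet Section 6.1 contains no safety monitoring, and Section 5.2 has no adverse-event item and no date or reason for COC discontinuation. The existing routes could catch some harms and stops, but only incidentally, and none captures the reason for a stop. The weakest stretch is the eight months after month 4.

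The size is about 70 to 75 exposed women if the equal split holds, and unknown otherwise. The documents state no length of COC treatment, so a full 12 months of exposure per woman should not be assumed. The conclusion rests on reading the interval history as undefined, which is how it stands in the schedule, and on there being no safety procedures in documents outside the supplied text. It does not depend on the sample-size calculation.

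**What to change.** - **Section 5.2:** add adverse events, serious adverse events, and date and reason for COC discontinuation.
- **Section 4.0 schedule:** ask about these at the existing month-4 visit and one-year call, and define the interval history so that it covers them. State when diaries are reviewed after month 4.
- **Section 6.1:** name the existing study role that reviews these data, or cross-refer to the procedure if it is held elsewhere.
- **Section 7.1 (Study Outcome Measures):** tabulate them descriptively by the three enrolment categories, without formal testing.

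A brief question at the existing weekly contacts is optional. It would detect events sooner, but for 150 athletes could mean up to 150 × 52 = 7,800 askings a year, in a training room where privacy is limited.

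Without the weekly question, the cost is a few form fields, one set of questions at two contacts already planned, some review time, and slightly more data entry and reporting. No dose or clinical rule changes.

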6.2 Quality Control and Quality Assurance

- [name] will be responsible for the evaluation, analysis, and reporting of the data among the co-investigators.

7.0 STATISTICAL CONSIDERATIONS

7.1 Study Outcome Measures

- **Data Analysis:** Statistical analysis will be performed using SAS statistical software (SAS Institute Inc., Cary, NC, USA) with significance set at $p<0.05$. Differences in the two timepoints will be evaluated between the two groups. Multiple regression will be used to analyze rate of injury as a function of OC use (group), joint laxity, motion analysis, and serum relaxin, and additional demographic data. Post-hoc ANOVA, or non-parametric alternative, will be used to evaluate continuous variables (joint laxity, motion analysis, and serum relaxin levels) between groups.
- Serum relaxin-2 level will be measured using a Quantikine Human Relaxin-2 Immunoassay (DRL200). All samples will be run in duplicate and relaxin-2 concentrations will be calculated from the standard curve. The intra-assay and inter-assay coefficients of variation and minimum detection limit will be determined and reported.
- Joint laxity measurements will be evaluated using the KT-2000 and the Beighton Score. The KT-2000 measures anterior and posterior displacement (mm) of the tibia relative to the femur when an anterior and posterior load are applied to the tibia. The amount of tibial displacement provides information on ACL laxity. The Beighton score is screening technique for measuring generalized joint hypermobility.¹ It requires the performance of 5 maneuvers, four passive bilateral and one active unilateral performance:
 1. Passive dorsiflexion and hyperextension of the fifth MCP joint beyond 90°
 2. Passive apposition of the thumb to the flexor aspect of the forearm
 3. Passive hyperextension of the elbow beyond 10°
 4. Passive hyperextension of the knee beyond 10°
 5. Active forward flexion of the trunk with the knees fully extended so that the palms of the hands rest flat on the floor

The Beighton score is based on a 9-point scale with ≥ 4 considered hypermobile.

- Continuous measures of trunk flexion, hip adduction, and internal/external and coronal plane rotation of the knee measured during a singled-legged drop using the motion tracking equipment mentioned above in section 4.0 (Aim 2). These outcomes measures are all in angles (degrees). Increased valgus knee motion (in the coronal plane) and landing with the femur in adduction and internal rotation has been suggested to predispose athletes to injury when landing from a jump.¹⁰

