Do Combined Oral Contraceptives Protect Against Anterior Cruciate Ligament Injuries in Female Athletes?

April 28, 2025

[name] MD¹, [name], MA², [name] PhD¹

¹ Kerlan Jobe Orthopedic Institute

² Cedars-Sinai Department of Obstetrics and Gynecology

TABLE OF CONTENTS

PROTOCOL SUMMARY	3
GENERAL INFORMATION	3
1.0 BACKGROUND, RATIONALE	4
2.0 STUDY OBJECTIVES	4
3.0 STUDY POPULATION	5
3.1 Selection of the Study Population	5
3.2 Inclusion Criteria	5
3.3 Exclusion Criteria	5
3.4 Subject Recruitment	5
3.5 Subject Screening and Enrollment	5
4.0 STUDY DESIGN AND METHODS	6
5.0 DATA COLLECTION AND MANAGEMENT	7
5.1 Data Procurement	8
5.2 Variables Collected	8
5.3 Source Documents	8
5.4 Data Collection and Storage	8
5.5 Confidentiality and Security of Data	8
6.0 DATA AND SAFETY MONITORING	8
6.1 Data and Safety Monitoring Plan	9
6.2 Quality Control and Quality Assurance	9
7.0 STATISTICAL CONSIDERATIONS	9
7.1 Study Outcome Measures	9
7.1 Sample Size Considerations	10
8.0 REFERENCES	10

PROTOCOL SUMMARY

Purpose and Knowledge to be Gained	
 The purpose of this study is to investigate the impact of combined oral contraceptive (COC) use on serum relaxin levels, ACL laxity, and rate of ligamentous injury among collegiate female athletes Previous research suggests COC use may decrease serum relaxin levels, which could decrease ACL laxity and potentially protect against ACL injury (which is disproportionately higher in female athletes vs male athletes)
Research Procedures	
 Assessment of baseline contraceptive status and initiation of study COC if participant desires Participants will undergo the following assessments at baseline and at the four-month time point 
 (1) Serum relaxin level (2) Knee joint anterior and posterior laxity will be tested using a KT-2000 arthrometer (Medmetric Corp, San Diego, CA) (3) Motion Tracking Analysis (4) Reported knee injury during study time period
Subject Population	
 150 female collegiate athletes competing in sports considered high-risk for ACL tears (basketball, soccer, and volleyball) Recruited from surrounding universities (Loyola Marymount, Pepperdine) where Cedars-Sinai Kerlan Jobe-affiliated orthopedic surgeons practice Participants who want to remain on no hormonal contraception or want to take study COC

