1.0 BACKGROUND, RATIONALE

Increased female athletic participation was set forth after the establishment of Title IX.¹¹ With this increase in activity came a dramatic rise in ACL injuries, revealing a significant gender disparity with women having a 2-to-10 times greater risk of ACL rupture.⁹ While numerous studies have revealed anatomic, neuromuscular and hormonal differences play a role,^{3, 6, 7} one question that has not fully been addressed is the possible protective role of combined oral contraceptives (COCs).

Prevalence of COC use among female athletes has been estimated at 40% to 50%, showing a significant acceptance of COC use by many female athletes.^{2, 12} Previous literature suggests that fluctuating hormones not only play a role in weakening the structure of the female ACL but also increase knee joint laxity, leading to poorer lower extremity biomechanics during sports and activities.^{5, 6} While some risk factors are not modifiable, such as the size of a woman's ACL or femoral notch, the ability to safely alter a female's hormonal profile to confer a more protective, favorable environment may theoretically provide a viable intervention for the female athletic community in ACL injury prevention as well as in post-ACL reconstruction rehabilitation.

Thus, advancing our knowledge of the underlying pathophysiological mechanisms of ACL injuries will further the development of prevention, rehabilitation and training strategies to reduce the risk of sport-related injury, thereby enhancing the beneficial effects of physical activity on women's health for all ages. With 4 out of 5 heterosexually active women in the U.S. using COC in their lifetime, this research may also contribute to growing evidence of non-contraceptive benefits of COCs.

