2.0 STUDY OBJECTIVES

We plan to investigate the hypothesis that combined oral contraceptives (COCs) reduce serum relaxin levels and ligament laxity in collegiate female athletes. Though this study cannot prove causality, we will also observe if rate of ligamentous injury in female athletes is reduced among women taking COC. Our specific aims are as follows:

Aim 1: To evaluate relaxin levels in female athletes on COC or no hormonal contraceptive

Aim 2: To quantify anterior and coronal plane (varus/valgus) knee laxity between female athletes using combined oral contraceptives and those who are not using any hormonal treatment.

Aim 3: To track the rate of ACL and other ligamentous injuries (ruptures / sprains) among female athletes and determine if COCs have a protective effect.

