3.2 Inclusion Criteria

- Female
- 18 years of age or older
- Currently playing basketball, soccer, or volleyball at Loyola Marymount or Pepperdine
- If not currently on COC, regular menstrual cycle occurring every 21-35 days

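### The one named analysis of the primary injury outcome adjusts for relaxin, laxity and motion at an unstated visit; with month-4 or change values, its group term is not the 30% v 10% difference the study was sized on

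*Combined protocol and SAP*

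**What the plan says.** Section 7.1 Sample Size Considerations names the rate of ligament injury as the primary outcome. It plans 140 women in equal groups for about 80% power to detect 10% with OC against 30% without.

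Section 7.1 Study Outcome Measures gives injury one method: "Multiple regression will be used to analyze rate of injury as a function of OC use (group), joint laxity, motion analysis, and serum relaxin", together with demographic data. The other named method, ANOVA or a non-parametric alternative, is limited to the continuous measures. A further sentence says that differences between the two timepoints will be compared between groups, but names neither an outcome nor a method.

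The same covariates appear elsewhere as consequences of COC use:

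- Protocol Summary: "Previous research suggests COC use may decrease serum relaxin levels, which could decrease ACL laxity and potentially protect against ACL injury".
- Section 1.0, on fluctuating hormones: they "increase knee joint laxity, leading to poorer lower extremity biomechanics during sports and activities".
- Section 2.0, the hypothesis: "combined oral contraceptives (COCs) reduce serum relaxin levels and ligament laxity in collegiate female athletes". Aim 3 is to track injuries and "determine if COCs have a protective effect".

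Section 4.0 lists relaxin, laxity and motion at baseline and at month 4, and counts injuries throughout the study. It also says "Orthopedic testing will start during the fourth menstrual/COC cycle due to delay in COC effect", which does not fit the baseline laxity and motion tests listed in the same section.

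**The concern.** A variable that the exposure is expected to change, and that is expected to change the outcome, lies on the path between them. Holding it fixed removes that part of the effect from the group term. Aim 3 and the sample size concern the overall difference in injury between groups. If the protocol's own hypothesis is right, a model containing month-4 relaxin and laxity would tend to hide the effect the study is looking for.

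The plan does not commit to month-4 or change values, but nothing in section 7.1 excludes them. One sentence therefore permits several models that answer different questions about the primary outcome, and the choice among them could be made after the data are seen. The stated power belongs to only one of those questions.

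Two further problems follow from the timing:

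- Women already on hormonal contraception who switch to the study COC (category 3 in section 4.0, number unknown) may have baseline values that already reflect exposure.
- An injury in the first months comes before the month-4 value that is supposed to explain it.

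**Working it through.** **1. Reproduce the plan's figure.** Inputs from section 7.1: risks 0.30 and 0.10, 70 per group, alpha 0.05 (two-sided assumed, as sidedness is not stated).

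- Pooled normal formula: power = Φ[(0.20 − 1.96·√(2·0.2·0.8/70)) / √((0.3·0.7 + 0.1·0.9)/70)] = Φ[(0.200 − 0.1325)/0.0655] = Φ(1.03) = 84.9%.
- With continuity correction, subtracting 1/70 from the difference: Φ(0.81) = 79.2%.
- Fisher's exact test: 81.3%.

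The stated figure of about 80% is thus reproduced as an unadjusted comparison of two proportions. Expected events are 70·0.30 + 70·0.10 = 28.

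**2. What the group term estimates.** Let logit P(injury) = a + g·group + b·M, where COC lowers the mediator M by d SD. The overall group effect on this scale is g − b·d. A model containing M reports g only, so b·d is lost. The mediated share is b·d/(b·d − g). For example, with d = 1 and a mediator-injury odds ratio (OR) of 2.0 per SD, b·d = ln 2.0 = 0.693 and g = ln 0.47 = −0.755. The share is 0.693/1.448 = 48%.

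**3. Size, as an illustration.** The shift d, the mediator-injury OR, the baseline/month-4 correlation (0.7) and the logistic form are assumptions; the documents give none of them. Setting: 70 per group, a and g solved so that marginal risks stay at 30% and 10%, one composite mediator, no confounding, two-sided Wald test, 4,000 replicates per setting. Group only gives power of about 85% and an OR of about 0.25.

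| Mediator-injury OR per SD | COC shift (SD) | Mediated share | Power, group + month-4 | Group OR, group + month-4 | Power, group + change |
|---|---|---|---|---|---|
| 1.5 | 0.25 | 7% | 79% | 0.27 | 82% |
| 1.5 | 0.5 | 15% | 71% | 0.30 | 76% |
| 1.5 | 1 | 29% | 47% | 0.37 | 56% |
| 2.0 | 0.25 | 12% | 78% | 0.27 | 80% |
| 2.0 | 0.5 | 24% | 62% | 0.32 | 71% |
| 2.0 | 1 | 48% | 28% | 0.47 | 48% |

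Independent repeats agreed to within about 3 points. Group plus a true pre-exposure baseline value keeps power at 85-86%.

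**4. How much is mere collinearity.** With no mediation at all, adding the month-4 value gives 85/83/77% at shifts of 0.25/0.5/1 SD. At 1 SD and OR 2.0, about 8 points of the fall from 85% to 28% (85 − 77) therefore come from correlation between group and mediator. The rest is a change in what is being estimated.

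**5. Direction.** Take no mediation, a 1 SD shift, and one unmeasured cause of injury (OR 2.0 per SD) that correlates with the mediator. The group OR after month-4 adjustment is 0.34 if that correlation is +0.5 and 0.18 if it is −0.5, against 0.25-0.26 for group only. The distortion can go either way.

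**The case against.** The strongest reply is that the harm is conditional. It requires month-4 or change values, a COC effect on the covariates, and a covariate effect on injury; the plan commits to none of the first. Section 2.0 also concedes "Though this study cannot prove causality". The conditionality is real. But the second and third conditions are the protocol's own hypothesis for relaxin and laxity, and the first is left open by the text. Disclaiming causality does not define the primary estimate.

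Other points, and what stands of each:

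- *Another analysis may cover injury.* The Protocol Summary lists reported knee injury among the two-timepoint assessments, so the sentence on timepoint differences could be read to include it. That sentence gives no method, so the regression remains the only analysis that names injury.
- *Motion is a weak mediator.* This stands. Section 2.0 names only relaxin and laxity, and section 1.0 links biomechanics to hormones only through laxity.
- *The plan adjusts for demographics, sensibly so for self-selected groups.* Also true. A pre-listed set of pre-exposure factors can keep them.
- *The sentence delaying orthopedic testing looks like a drafting slip.* Probably so, but it must still be reconciled with the baseline tests.
- *The losses depend wholly on assumed inputs, and the 85% benchmark is not the plan's 80%.* Both are fair. The 79-85% range for the unadjusted comparison reflects choice of test, and the loss is small at a 0.25 SD shift.
- *One composite covariate understates the overfitting.* Correct. Relaxin (1), laxity (3), motion (4) and group make nine terms before demographics, against about 28 events.

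**Conclusion.** The concern holds and should be fixed. The documents alone establish three things: the regression is the only named injury analysis, the visit supplying its covariates is unstated, and the stated power belongs to a different, unadjusted comparison. It also follows from the protocol's own rationale that month-4 or change values would take the group term away from the overall 30% v 10% difference.

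How much is lost cannot be read from the documents. Under the assumptions above it ranges from minor (78-79% power at 0.25 SD) to severe (28-47% at 1 SD) for the month-4 model, and self-selection means the bias could run in either direction. Baseline values avoid the problem only for women not yet exposed, so simply declaring that baseline values will be used is an incomplete repair while category 3 is included.

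**What to change.** Reword section 7.1 Study Outcome Measures before any data are examined:

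1. Name as the primary injury analysis the comparison of COC with no hormonal contraception, adjusted only for a short pre-listed set of pre-exposure factors such as sport (and any demographics the sponsor wishes to keep), with no relaxin, laxity or motion values. The method should tolerate few or no events within a sport, since the sample-size section cites 0% for volleyball; Mantel-Haenszel or Firth logistic regression are examples, at the statistician's choice. The injury definition stays as the sponsor sets it.
2. Move relaxin, laxity and motion to a separate exploratory mechanistic analysis that states the visit used and counts only injuries after that visit.
3. If baseline values of these measures are wanted as adjusters, make that a sensitivity analysis restricted to categories 1 and 2. First reconcile the section 4.0 sentence on when orthopedic testing starts with the baseline tests, and state the cycle timing of the baseline relaxin sample, which section 4.0 gives only for month 4.

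The cost is rewording and one extra model, with no new visits or tests. Sport is known from eligibility ("Currently playing basketball, soccer, or volleyball at Loyola Marymount or Pepperdine") but should be added to the variable list in section 5.2. The drawback is that the mechanistic model will rest on fewer than the roughly 28 events expected overall.
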